## 4. STUDY DESIGN

### 4.1. Overall Design

This will be a Phase 3, multicenter, randomized, double-blind third-party–unblinded study that will be conducted at investigator sites in Japan, Korea, and Taiwan.

Approximately 1400 participants 60 years of age and older who are pneumococcal vaccine naïve will be randomized into 2 vaccine groups in a 1:1 ratio. Each participant will receive either 20vPnC or 13vPnC (control vaccine) at Vaccination 1. Participants who received 20vPnC at Vaccination 1 will receive saline at Vaccination 2. Participants who received 13vPnC at Vaccination 1 will receive PPSV23 at Vaccination 2.

On Day 1 (Visit 1), participants will be assessed for eligibility, have blood drawn for immunogenicity assessments, and receive 20vPnC or 13vPnC administered by blinded site staff. Participants will be observed for at least 30 minutes after vaccination by blinded site staff, who will record AEs occurring during that time. Participants will also receive safety follow-up and e-diary instructions at the visit. Prompted systemic events (fever, headache, fatigue, muscle pain, and joint pain) occurring within 7 days after vaccination (where Day 1 is the day of vaccination) and prompted local reactions (redness, swelling, and pain at the injection site) occurring at the 20vPnC or 13vPnC injection site within 10 days after vaccination (where Day 1 is the day of vaccination) will be collected daily in the e-diary. Use of antipyretic/pain medications will be collected daily in an e-diary for 7 days after vaccination (where Day 1 is the day of vaccination). Participants will be instructed to contact the study staff if the participant experiences redness or swelling at the 20vPnC/saline injection site measuring >20 measuring device units (>10 cm) or severe injection site pain (prevents daily activity) in the 10 days after vaccination or has an emergency room visit or hospitalization.

Participants will return for Visit 2 (28 to 42 days after Visit 1), and information will be collected from the participants on AEs, SAEs, and e-diary follow-up (as needed). Participants will also be asked for information on concomitant medications used to treat any SAEs and on any nonstudy vaccines they received since Visit 1. Blood will be drawn for immunogenicity assessments. Saline will be administered to participants who previously received 20vPnC, and PPSV23 will be administered to participants who previously received 13vPnC, by a third-party unblinded site staff member. Participants will be observed for at least 30 minutes after vaccination by blinded site staff, who will record AEs occurring during that time. Participants will also be reminded about safety follow-up. The control participants are receiving a schedule that has been studied previously with no safety concerns, but it is a research schedule and a specific request has been made by the PMDA to collect additional information in the Japanese population. For participants enrolled at **Japan sites**, prompted local reactions occurring at the saline and PPSV23 injection site within 10 days after vaccination and prompted systemic events occurring within 7 days after vaccination will be collected daily in the e-diary. Use of antipyretic/pain medications will be collected daily in an e-diary for 7 days after vaccination.

Participants will return for Visit 3 (28 to 42 days after Visit 2) and information will be collected from the participants on AEs and SAEs. Participants will also be asked for information on concomitant medications used to treat any SAEs and on any nonstudy vaccines they received since Visit 2. Blood will be drawn for immunogenicity assessments.

#### **4.1.1. Approximate Duration of Participation for Each Participant**

Each participant will participate in the study for approximately 2 months. Based on an 8-month enrollment period, the study duration will be approximately 10 months.

#### **4.1.2. Approximate Number of Participants**

Approximately 1400 participants will be enrolled to achieve a target of 1260 evaluable participants (630 participants in each vaccine group) (assuming a 10% nonevaluable rate). Approximately 700 participants will be enrolled from Japan, approximately 500 from Korea, and approximately 200 from Taiwan. The study will target enrolment of 50 %, or more, adults  $\geq 65$  years of age in each country. Note however, that the enrolment targets are approximations, and may not be achieved, particularly for the older age group. Randomization into the 2 vaccine groups will be managed within the age stratification (50 to 64 years of age and  $\geq 65$  years of age).

Note: "Enrolled" means a participant's agreement to participate in a clinical study following completion of the informed consent process. Potential participants who are screened for the purpose of determining eligibility for the study, but do not participate in the study, are not considered enrolled, unless otherwise specified by the protocol.

#### **4.2. Scientific Rationale for Study Design**

The purpose of this study is to assess the safety and immunogenicity of 20vPnC in adults  $\geq 60$  years of age in Japan, Korea, and Taiwan [REDACTED] CCI [REDACTED]

[REDACTED] This study uses a similar design and includes similar assessments as in prior studies of 20vPnC in adults (B7471002 and B7471007).

Human reproductive safety data are not available for 20vPnC, but there is no suspicion of human teratogenicity based on the intended pharmacology of the compound. Therefore, the use of a highly effective method of contraception is required [REDACTED] CCI [REDACTED]

#### **4.3. Justification for Dose**

The 20vPnC candidate is modeled after 7vPnC and 13vPnC, and contains capsular polysaccharides from pneumococcal serotypes 1, 3, 4, 5, 6A, 6B, 7F, 8, 9V, 10A, 11A, 12F, 14, 15B, 18C, 19A, 19F, 22F, 23F, and 33F individually conjugated to CRM197. The vaccine formulation contains 2.2  $\mu$ g of each saccharide, except for 4.4  $\mu$ g of 6B, per 0.5-mL dose. In adults, administration of 1 dose of pneumococcal conjugate vaccine induces immune responses.

For this product, the term "dose" refers to an injection of a vaccine.

#### **4.4. End of Study Definition**

The end of the study is defined as the date of the last visit of the last participant in the study.

### **5. STUDY POPULATION**

This study can fulfill its objectives only if appropriate participants are enrolled. The following eligibility criteria are designed to select participants for whom participation in the study is considered appropriate. All relevant medical and nonmedical conditions should be taken into consideration when deciding whether a particular participant is suitable for this protocol.

Prospective approval of protocol deviations to recruitment and enrollment criteria, also known as protocol waivers or exemptions, is not permitted.

#### **5.1. Inclusion Criteria**

Participants are eligible to be included in the study only if all of the following criteria apply:

##### **Age and Sex:**

1. Male or female participants  $\geq 60$  years of age at the time of consent.
  - Refer to Appendix 4 for reproductive criteria for male ([Section 10.4.1](#)) and female ([Section 10.4.2](#)) participants.

##### **Type of Participant and Disease Characteristics:**

2. Participants who are willing and able to comply with all scheduled visits, treatment plan, lifestyle considerations, and other study procedures.
3. Expected to be available for the duration of the study and can be contacted by telephone during study participation.
4. Adults determined by clinical assessment, including medical history and clinical judgment, to be eligible for the study, including adults with preexisting stable disease, defined as disease not requiring significant change in therapy in the previous 6 weeks or hospitalization for worsening disease within 12 weeks before receipt of study intervention.

[For adults **60 through 64 years of age** to be enrolled **at Japan sites only**:]

- Participants must have a preexisting chronic stable disease with an elevated risk for pneumococcal disease (eg, chronic cardiac disease, chronic pulmonary disease, chronic hepatic disease, diabetes mellitus, and/or chronic renal disorders).

5. Female participants of nonchildbearing potential or male participants not able to father children; male participants who are able to father children and willing to use a highly

effective method of contraception as outlined in this protocol until at least 28 days after the last dose of study intervention.

COI

**Weight:**

Not applicable.

**Informed Consent:**

6. Capable of giving signed informed consent as described in [Appendix 1](#), which includes compliance with the requirements and restrictions listed in the ICD and in this protocol.

**5.2. Exclusion Criteria**

Participants are excluded from the study if any of the following criteria apply:

**Medical Conditions:**

1. History of severe adverse reaction associated with a vaccine and/or severe allergic reaction (eg, anaphylaxis) to any component of 20vPnC, 13vPnC, or any other diphtheria toxoid-containing vaccine or PPSV23.
2. Serious chronic disorder, including metastatic malignancy, severe COPD requiring supplemental oxygen, end-stage renal disease with or without dialysis, cirrhosis of the liver, clinically unstable cardiac disease, or any other disorder that, in the investigator's opinion, excludes the participant from participating in the study.
3. History of microbiologically proven invasive disease caused by *S pneumoniae*.
4. Known or suspected immunodeficiency or other conditions associated with immunosuppression, including, but not limited to, immunoglobulin class/subclass deficiencies, generalized malignancy, HIV infection, leukemia, lymphoma, or organ or bone marrow transplant.
5. Bleeding diathesis or condition associated with prolonged bleeding that would, in the opinion of the investigator, contraindicate intramuscular injection.
6. Pregnant female participants or breastfeeding female participants (known or suspected).
7. Congenital, functional, or surgical asplenia.
8. Other medical or psychiatric condition including recent (within the past year) or active suicidal ideation/behavior or laboratory abnormality that may increase the risk of study

participation or, in the investigator's judgment, make the participant inappropriate for the study.

**Prior/Concomitant Therapy:**

9. Previous vaccination with any licensed or investigational pneumococcal vaccine, or planned receipt through study participation.
10. Currently receives treatment with immunosuppressive therapy, including cytotoxic agents or systemic corticosteroids, or planned receipt through the last blood draw. If systemic corticosteroids have been administered short term (<14 days) for treatment of an acute illness, participants should not be enrolled into the study until corticosteroid therapy has been discontinued for at least 28 days before study intervention administration.  
Inhaled/nebulized, intra-articular, intrabursal, or topical (skin, eyes, or eyes) corticosteroids are permitted.
11. Receipt of blood/plasma products or immunoglobulin, from 60 days before study intervention administration, or planned receipt through study participation.

**Prior/Concurrent Clinical Study Experience:**

12. Participation in other studies involving investigational drug(s), investigational vaccines, or investigational devices within 28 days prior to study entry and/or during study participation. Participation in purely observational studies is acceptable.

**Diagnostic Assessments:**

Not applicable.

**Other Exclusions:**

13. Investigator site staff or Pfizer employees directly involved in the conduct of the study, site staff otherwise supervised by the investigator, and their respective family members.

**5.3. Lifestyle Considerations**

**5.3.1. Contraception**

The investigator or his or her designee, in consultation with the participant, will confirm that the participant has selected an appropriate method of contraception for the individual participant and his or her partner(s) from the permitted list of contraception methods **CCI** [REDACTED] and will confirm that the participant has been instructed in its consistent and correct use. At time points indicated in the SoA, the investigator or designee will inform the participant of the need to use highly effective contraception consistently and correctly and document the conversation and the participant's affirmation in the participant's chart (participants need to affirm their consistent and correct use of at least 1 of the selected methods of contraception). In addition, the investigator or designee will instruct the

participant to call immediately if the selected contraception method is discontinued or if pregnancy is known or suspected in the participant or partner.

#### **5.4. Screen Failures**

Screen failures are defined as participants who consent to participate in the clinical study but are not subsequently randomly assigned to study intervention/enrolled in the study. A minimal set of screen failure information is required to ensure transparent reporting of screen failure participants to meet the CONSORT publishing requirements and to respond to queries from regulatory authorities. Minimal information includes demography, screen failure details, eligibility criteria, and any AEs and SAEs.

Individuals who do not meet the criteria for participation in this study (screen failure) may not be rescreened.

#### **5.5. Criteria for Temporarily Delaying Enrollment/Randomization/Study Intervention Administration**

The following conditions are temporary or self-limiting and a participant may be vaccinated in the study once the condition(s) has/have resolved and no other exclusion criteria are met.

The Visit 1 and Visit 2 blood draws prior to Vaccination 1 and Vaccination 2 should take place on the same day as the vaccination.

- Current febrile illness (body [oral] temperature  $\geq 38^{\circ}\text{C}$ , or  $\geq 37.5^{\circ}\text{C}$  for participants from Japan sites) or other acute illness within 48 hours before study intervention administration.
- Receipt of any inactivated or otherwise nonlive vaccine within 14 days or any live vaccine within 28 days before study intervention administration.
- Receipt of short-term (<14 days) systemic corticosteroids. Study intervention administration should be delayed until systemic corticosteroid use has been discontinued for at least 28 days. Inhaled/nebulized, intra-articular, intrabursal, or topical (skin or eyes) corticosteroids are permitted.

### **6. STUDY INTERVENTION**

Study intervention is defined as any investigational intervention(s), marketed product(s), placebo, medical device(s), or study procedure(s) intended to be administered to a study participant according to the study protocol.

For the purposes of this protocol, study intervention refers to 20vPnC, 13vPnC, PPSV23, and placebo.

## 6.1. Study Intervention(s) Administered

20vPnC contains saccharides from pneumococcal serotypes 1, 3, 4, 5, 6A, 6B, 7F, 8, 9V, 10A, 11A, 12F, 14, 15B, 18C, 19A, 19F, 22F, 23F, and 33F individually conjugated to CRM197. **CCI**

13vPnC contains saccharides from pneumococcal serotypes 1, 3, 4, 5, 6A, 6B, 7F, 9V, 14, 18C, 19A, 19F, and 23F individually conjugated to CRM197. **CCI**

20vPnC and 13vPnC will be supplied to the site as packaged, single-use PFSs and labeled according to local regulatory requirements.

PPSV23 is a licensed commercial product and is a clear, sterile solution consisting of a mixture of purified capsular polysaccharides from 23 serotypes of *S pneumoniae*: 1, 2, 3, 4, 5, 6B, 7F, 8, 9N, 9V, 10A, 11A, 12F, 14, 15B, 17F, 18C, 19F, 19A, 20, 22F, 23F, and 33F. The vaccine is formulated to contain 25 µg of each of the 23 purified polysaccharide serotypes per 0.5-mL dose of vaccine in an isotonic saline solution containing 0.25% phenol as a preservative. PPSV23 will be supplied by the sponsor to the site as packaged vials or PFSs and labeled according to local regulatory requirements.

The placebo will consist of a sterile normal saline solution for injection (0.9% sodium chloride injection) and will be supplied to the site as packaged vials or PFSs and labeled according to local regulatory requirements.

### 6.1.1. Administration

At Vaccination 1 (Visit 1), a 0.5-mL dose of 20vPnC or 13vPnC will be administered intramuscularly in the deltoid muscle of the nondominant arm by a blinded site staff member (20vPnC and 13vPnC have the same appearance).

At Vaccination 2 (Visit 2), a 0.5-mL dose of saline or PPSV23 will be prepared and administered by third-party unblinded site staff member(s) and will be administered intramuscularly in the deltoid muscle of the nondominant arm to blinded participants. All other study personnel, including the PI, and the participant, will be blinded. The unblinded site staff members will not participate in participant assessments.

Standard vaccination practices must be observed and vaccine must not be injected into blood vessels. Appropriate medication and other supportive measures for management of an acute hypersensitivity reaction should be available in accordance with local guidelines for standard immunization practices.

Administration of study interventions should be performed by an appropriately qualified, GCP-trained, and vaccine-experienced member of the study staff (eg, physician, nurse, physician's assistant, nurse practitioner, pharmacist, or medical assistant) as allowed by local, state, and institutional guidance.

Study intervention administration details will be recorded on the CRF.

#### **6.1.2. Medical Devices**

[figure not shown]
1. In this study, medical devices being deployed are the PFSSs used to contain 20vPnC, 13vPnC, and saline.
2. Other medical devices (not manufactured by or for the sponsor) provided for use in this study are syringes for PPSV23.
3. Instructions for medical device use are provided in the IP manual.
4. All medical device deficiencies (including malfunction, use error, and inadequate labeling) shall be documented and reported by the investigator throughout the clinical investigation (see [Section 8.3.9](#)) and appropriately managed by the sponsor.

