### **8.3.9. Medical Device Deficiencies**

Medical devices are being provided for use in this study for the purpose of administering the study intervention. In order to fulfill regulatory reporting obligations worldwide, the unblinded site staff is responsible for the detection and documentation of events meeting the definitions of device deficiency that occur during the study with such devices.

The definition of a medical device deficiency can be found in [Appendix 8](#).

NOTE: Deficiencies fulfilling the definition of an AE/SAE will also follow the processes outlined in [Section 8.3.1](#) through [Section 8.3.4](#) and [Appendix 3](#).

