### 8.3.9.2. Follow-up of Medical Device Deficiencies

Follow-up applies to all participants, including those who discontinue study intervention.

The unblinded site staff is responsible for ensuring that follow-up includes any supplemental investigations as indicated to elucidate the nature and/or causality of the deficiency.

New or updated information will be recorded on a follow-up form with all changes signed and dated by the unblinded site staff.

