### 8.3.9.3. Prompt Reporting of Device Deficiencies to Sponsor

Device deficiencies will be reported to the sponsor within 1 day after the unblinded site staff determines that the event meets the protocol definition of a medical device deficiency.

Information will be provided to the sponsor as described in the IP manual. The medication error CRF will also be completed.

Any device deficiency that is associated with an SAE must be reported to Pfizer Safety within 24 hours upon the investigator's awareness as outlined in [Section 8.3.1.1](#) and [8.3.1.2](#).

The sponsor will be the contact for the receipt of device deficiency information.

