### **10.8.4. Recording/Reporting and Follow-up of AEs and/or SAEs and Device Deficiencies**

#### **AE, SAE, and Device Deficiency Recording**

- When an AE/SAE/device deficiency occurs, it is the responsibility of the investigator to review all documentation (eg, hospital progress notes, laboratory reports, and diagnostic reports) related to the event.
- The investigator will then record all relevant AE/SAE/device deficiency information in the participant's medical records, in accordance with the investigator's normal clinical practice and on the appropriate form of the CRF.
- It is **not** acceptable for the investigator to send photocopies of the participant's medical records to Pfizer Safety in lieu of following the reporting process described in the IP manual and completing the Medication Error CRF.
- There may be instances when copies of medical records for certain cases are requested by Pfizer Safety. In this case, all participant identifiers, with the exception of the participant number, will be redacted on the copies of the medical records before submission to Pfizer Safety.
- The investigator will attempt to establish a diagnosis of the event based on signs, symptoms, and/or other clinical information. Whenever possible, the diagnosis (not the individual signs/symptoms) will be documented as the AE/SAE.

- For device deficiencies, it is very important that the investigator describes any corrective or remedial actions taken to prevent recurrence of the incident.
  - A remedial action is any action other than routine maintenance or servicing of a medical device where such action is necessary to prevent recurrence of a device deficiency. This includes any amendment to the device design to prevent recurrence.

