### Assessment of Causality

- The investigator is obligated to assess the relationship between study intervention and each occurrence of each AE/SAE/device deficiency.
- A “reasonable possibility” of a relationship conveys that there are facts, evidence, and/or arguments to suggest a causal relationship, rather than a relationship cannot be ruled out.
- The investigator will use clinical judgment to determine the relationship.
- Alternative causes, such as underlying disease(s), concomitant therapy, and other risk factors, as well as the temporal relationship of the event to study intervention administration will be considered and investigated.
- The investigator will also consult the IB and/or product information in his/her assessment.
- For each AE/SAE/device deficiency, the investigator **must** document in the medical notes that he/she has reviewed the AE/SAE/device deficiency and has provided an assessment of causality.
- There may be situations in which an SAE has occurred and the investigator has minimal information to include in the initial report to the sponsor. However, it is very important that the investigator always make an assessment of causality for every event before the

initial transmission of the SAE data to the sponsor.

- The investigator may change his/her opinion of causality in light of follow-up information and send an SAE follow-up report with the updated causality assessment.
- The causality assessment is one of the criteria used when determining regulatory reporting requirements.

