### **Follow-up of AE/SAE/Device Deficiency**

- The investigator is obligated to perform or arrange for the conduct of supplemental measurements and/or evaluations as medically indicated or as requested by the sponsor to elucidate the nature and/or causality of the AE/SAE/device deficiency as fully as possible. This may include additional laboratory tests or investigations, histopathological examinations, or consultation with other healthcare providers.
- If a participant dies during participation in the study or during a recognized follow-up period, the investigator will provide Pfizer Safety with a copy of any postmortem findings including histopathology.
- New or updated information will be recorded in the originally completed CRF.
- The investigator will submit any updated SAE data to the sponsor within 24 hours of receipt of the information.

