### **10.8.6. Reporting of SADEs**

#### **SADE Reporting to Pfizer Safety**

NOTE: There are additional reporting obligations for medical device incidents that are potentially related to SAEs that must fulfill the legal responsibility to notify appropriate regulatory authorities and other entities about certain safety information relating to medical devices being used in clinical studies.

- Any device deficiency that is associated with an SAE must be reported to the sponsor within 24 hours after the investigator determines that the event meets the definition of a device deficiency.
- The sponsor shall review all device deficiencies and determine and document in writing whether they could have led to an SAE. These shall be reported to the regulatory authorities and IRBs/ECs as required by national regulations.

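### Does it matter that the protocol gives device-deficiency records to the blinded investigator in one place and to unblinded site staff in another?

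*Protocol*

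**What the plan says.** Three parts of the protocol deal with device deficiencies.

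- **Section 6.1.2** places the duty on the investigator: "All medical device deficiencies (including malfunction, use error, and inadequate labeling) shall be documented and reported by the investigator throughout the clinical investigation". The sentence then points to Section 8.3.9.
- **Section 8.3.9** says that "the unblinded site staff is responsible for the detection and documentation of events meeting the definitions of device deficiency that occur during the study". On follow-up, 8.3.9.2 states: "New or updated information will be recorded on a follow-up form with all changes signed and dated by the unblinded site staff". On timing, 8.3.9.3 states: "Device deficiencies will be reported to the sponsor within 1 day after the unblinded site staff determines that the event meets the protocol definition". Section 8.3.9.1 sends the reader to Appendix 8 for the method of documentation.
- **Appendix 8** returns to the investigator. On recording: "The investigator will then record all relevant AE/SAE/device deficiency information". On causality: "The investigator is obligated to assess the relationship between study intervention and each occurrence of each AE/SAE/device deficiency". On updates: "New or updated information will be recorded in the originally completed CRF". For deficiencies linked to an SAE, 10.8.6 starts the clock "within 24 hours after the investigator determines that the event meets the definition of a device deficiency".

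Section 6.3.2 blinds the principal investigator and everyone who does assessments, data collection or CRF entry. It keeps the unblinded staff who give the second injection out of participant assessments. Section 6.3.4 keeps the investigator blinded for the whole study.

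**The concern.** The investigator is blinded and the third-party staff are not, so no single person can fill both roles. Read literally, a site seems to face a choice. Either a blinded investigator handles a device record, or unblinded staff take on CRF and assessment work that 6.3.2 reserves for blinded staff.

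Visit 2 is where this could matter. The groups then receive different products, and Section 6.1.2 lists prefilled syringes for saline separately from the syringes for PPSV23. A record naming the device might therefore show the group to someone who still judges AE severity and causality up to Visit 3. Visit 1 raises a different question. Blinded staff give that injection, so it is unclear who plays the unblinded role named in 8.3.9.

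Two smaller points sit nearby. The last bullet of Section 8.11.2, on completing the CRF and the accountability records, does not say whether blinded or unblinded staff do it. SAP Section 2.2 allows blinded or unblinded staff to vaccinate at Visit 1, where Protocol 4.1 and 6.1.1 say blinded.

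**Working it through.** The plan states no figure on this point, so the check is mainly a comparison of texts.

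**1. Section 8.3.9 against Appendix 8, task by task**

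| Task | Section 8.3.9 | Appendix 8 | Result |
|---|---|---|---|
| Document the deficiency | Unblinded staff | Investigator, in medical records and CRF | Conflict |
| Arrange follow-up enquiries | Unblinded staff | Investigator | Conflict |
| Record updates | Separate form, signed by unblinded staff | Original CRF | Conflict |
| Grade intensity, judge causality | Silent | Investigator | One text only |
| Route to the sponsor | Investigational product manual and medication error CRF | The same | Agree |
| Clock, no SAE | Unblinded staff determine; 1 day | Silent | One text only |
| Clock, SAE-linked | Investigator's awareness; 24 hours | Investigator's determination; 24 hours | Same role, different trigger |

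Three of the seven rows conflict on role or form. Section 6.1.2 adds no further conflict, because its cross-reference lets it be read as general investigator responsibility carried out through 8.3.9. The two SAE clocks can both be met: awareness cannot come after determination, so a report within 24 hours of awareness satisfies either text. Section 8.3.1.1 already requires every SAE to be reported within 24 hours of awareness.

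**2. Visit 1**

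Section 6.3.1 gives the unblinded third party the second administration, but does not say that such staff are absent from Visit 1. Section 6.3.2 calls for more than one of them and allows them to come from the site or the pharmacy. Who acts at Visit 1 is unclear, but the role is not missing. The 20vPnC and 13vPnC syringes look identical and come in blinded cartons, so no route to unblinding is shown at that visit.

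**3. How many sponsor syringes are involved**

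Sections 4.1 and 9.2 plan 1400 participants, 700 per group.

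- Visit 1: 1400 prefilled syringes of 20vPnC or 13vPnC.
- Visit 2, saline in syringes as Section 6.1.2 lists: 700. Total 1400 + 700 = 2100; Visit 1 share 1400/2100 = 67%.
- Visit 2, saline in vials as Section 6.1 also allows: 0. Total 1400; Visit 1 share 100%.

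So between two thirds and all of these syringes are used where the products look alike. The documents give no deficiency rate, so the number of records cannot be derived from them.

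**4. Would a Visit 2 record show the group?**

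Appendix 8 limits its procedures to sponsor devices, which would point to saline. Section 8.3.9.4, however, covers any device provided for the study, and Section 6.1 allows vials or prefilled syringes for both saline and PPSV23. The product manual, which governs the report, is not part of the public documents. What a given record would disclose is therefore not established.

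**5. Which results could be affected**

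- Noninferiority: Section 6.3.3 keeps the serology laboratory blinded, and the titers do not pass through the investigator's judgment.
- Primary safety: the endpoints are reactions within 10 or 7 days and AEs and SAEs within 1 month after the first injection. Section 8.11.2 collects events since Visit 1 before the second injection is given.
- Secondary safety (Japan sites): reactions after the second injection are entered by participants in the e-diary. Investigators enter at Grade 4 classification and unscheduled visits.

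**6. The two smaller points**

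The 8.11.2 bullet repeats the Visit 1 wording and leaves room for an authorized designee; it lacks a label but contradicts nothing. The SAP 2.2 clause concerns who vaccinates and has no bearing on device records.

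**The case for a change.** The strongest argument for a change is that delegation does not dissolve the conflict. Appendix 8 asks the investigator personally to grade and judge each deficiency. Unblinded staff cannot stand in, since 6.3.2 keeps them out of assessments and reserves CRF entry for blinded staff, while 8.3.9.3 itself calls for a CRF page. The sections cross-refer, so they cannot be treated as separate procedures. The investigator goes on judging AEs after Visit 2, and the Japan-site reactogenicity objective depends on that period. Aligning the wording would cost almost nothing.

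The textual part of this stands: 8.3.9 and Appendix 8 do disagree on who documents and follows up, and on which form. The consequence is not shown. To reach a result, a syringe must be deficient at Visit 2, the record must name the product, it must pass to a blinded assessor despite 6.3.2, and it must then alter that person's judgment of an event. The documents establish none of these steps. The results most open to such influence, AE severity and causality after Visit 2, are not primary endpoints and carry no hypothesis test.

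**Conclusion.** No change to the plan is needed. There is a genuine but editorial inconsistency between Section 8.3.9 and Appendix 8 over who documents and follows up a device deficiency, and on which form. A site can fill the gap within the blinding rules it already has: unblinded staff hold whatever identifies the Visit 2 product and report it through the product manual, while the blinded investigator deals with any associated event. Rewording would record this division of work without altering the design, data or analysis.

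The shown effect on the 20 noninferiority comparisons and on the primary safety endpoints is nil. For later, investigator-judged safety data no effect is demonstrated, and none can be sized without a deficiency rate. The conclusion assumes that sites apply Section 6.3.2 to device records as they do to other study records, and that the unseen product manual does not direct product-identifying details to blinded staff.
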